## Protocol

The protocol recommended tactile assessments of the adductor pollicis TOF count, if feasible, and intraoperative muscle relaxation according to surgical requirement. All rocuronium doses were calculated using ideal body weight (IBW). Previous studies indicate that NMBDs are more appropriately dosed based on IBW than on actual body weight, 12 and high BMI has been identified as a risk factor for PRNB.13 IBW was calculated by using the Devine formula as 50.0 + 0.9 kg cm-1 over 152 cm for males and 45.5 + 0.9 kg cm-1 over 152 cm for females, with intubation dose calculated as 0.6 mg kg-1 (IBW). Doses for women were reduced by 15%, as the ED95 is lower for females, leading to prolonged effects if given the same dose of rocuronium as males.14,15 We calculated an additional 1% dose reduction per year over 55 of age because of previous studies indicating a prolonged effect in older patients,15 with age being a known risk factor for PRNB.16 The protocol recommended avoiding deep block (complete absence of the TOF response) because there is conflicting evidence that deep block is of benefit.17 If there was a continued need for muscle relaxation, maintenance doses were recommended when the TOF count reached 3; each maintenance dose was calculated as 25% of the intubation dose rounded up to the next higher 5 mg, except during the last hour of the case when it was rounded down to the next lower 5 mg. At the end of the procedure, a tactile pre-reversal assessment of the thumb response to ulnar nerve stimulation was mandatory. If facial nerve stimulation and evaluation of eye-muscle twitches had been used intraoperatively, a change of monitoring site to ulnar nerve stimulation was conducted at the end of the procedure 18 to mitigate against eye-muscle monitoring as a significant risk factor for PRNB. 13 Reversal dose of neostigmine was calculated using ideal body weight (IBW) while the sugammadex dose was based on actual body weight. The protocol calls for a minimum of 10 minutes after neostigmine administration and minimum 3 minutes after sugammadex administration before tracheal extubation (Table 1).

Providers were trained regarding the implementation of the new protocol and instructed to follow the practice suggestions. The research staff assisted the providers with protocol reminders and dose calculations.

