## Study procedures

We had originally planned to use either acceleromyography (Stimpod 450, Xavant, Pretoria, South Africa) or electromyography for research measurements in this study. After trying electromyographic measurements for four patients in this study we observed that the new electromyographic monitors at our institutions had inconsistent performance. We therefore decided to exclusively use a Stimpod 450 acceleromyograph for all patients. This is a tri-axial acceleromyograph, and subsequently all measurements were obtained in the same manner for all patients. All measurements were normalized, as this is recommended when using acceleromyography.19 Two ECG surface electrodes were placed over the ulnar nerve at the wrist, with the positive electrode 3-4 cm proximal to the negative electrode. Immediately after induction of general anesthesia, and before any muscle relaxant had been administered, research staff obtained baseline TOFR measurements. The baseline and all other quantitative TOFR measurements were obtained by averaging two measurements separated by at least 15 s. If the initial two measurements were not within 10% agreement, additional measurements (up to four total) separated by at least 15 s were made and the two closest TOF ratios averaged. Anesthesia providers were blinded to all quantitative measurements. After baseline measurements, the research staff disconnected the Stimpod 450, but left the surface electrodes in place to be used for subsequent study measurements. Additional measurements were obtained in duplicate immediately before reversal when the anesthesia provider made the tactile pre-reversal assessment, immediately before tracheal extubation, and a final set of measurements were obtained within 5 min of arrival to the post anesthesia care unit (PACU).

Baseline measurements were used to normalize all subsequent measurements. This was done to correct for the inflated TOFR values that are usually obtained by acceleromyography. 20,21 As an example, if the baseline TOFR is 1.15 and the raw postoperative TOFR is 0.95, then the nTOFR is 0.95/1.15 =0.83. Normalization usually yields lower TOF ratios, and it is more likely to classify observations as positive for PRNB. Therefore, the incidence of PRNB is typically higher when comparing normalized to non-normalized (also referred to as "raw") measurements. PRNB was defined as a nTOFR <0.9 on arrival to the PACU.

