Study Title: Best Practice With Rocuronium, Neostigmine, Sugammadex, and Subjective Monitoring

NCT03543826

Document title: Statistical Analysis Plan

Date of the document: 5/8/2019

Statistical analysis

We present descriptive statistics [mean (standard deviation) or frequencies] for baseline measures of patient and surgery characteristics. The primary endpoint, incidence of PRNB (nTOFR <0.9) on arrival to the PACU, was calculated with exact binomial 95% confidence interval, and graphically displayed using scatterplots. The primary analysis was "per-protocol" and patients were excluded if the protocol was not followed. Secondary endpoints included severe PRNB, defined as nTOFR <0.7 on arrival to the PACU, and PRNB at time of tracheal extubation (nTOFR <0.9). These were also calculated with the exact confidence intervals. Additionally, we calculated the incidence of severe PRNB at time of tracheal extubation and the incidence of PRNB using raw (non-normalized) measurements.

We compared the duration between end of surgery and arrival to the PACU for patients whose tracheas were extubated in the OR and those extubated in PACU. We also compared the duration between end of surgery and arrival to the PACU for patients receiving sugammadex or neostigmine.

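### Could research staff who prompt the anesthesia providers and also take the concealed TOFR readings undo the blinding?

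*Protocol*

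**What the plan says.** Two statements about research staff sit in different sections of the Protocol document. The section Protocol, after describing how providers were trained, adds: "The research staff assisted the providers with protocol reminders and dose calculations". The section Study procedures gives the same group a measuring role. Its baseline sentence reads "before any muscle relaxant had been administered, research staff obtained baseline TOFR measurements", and then "the research staff disconnected the Stimpod 450, but left the surface electrodes in place to be used for subsequent study measurements".

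The later readings are described without an operator: "Additional measurements were obtained in duplicate immediately before reversal when the anesthesia provider made the tactile pre-reversal assessment, immediately before tracheal extubation", with a last set within 5 minutes of PACU arrival. Study procedures also contains the safeguard: "Anesthesia providers were blinded to all quantitative measurements".

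Two further statements bear on the question. The section Protocol sets lower limits on the interval between reversal and extubation: "The protocol calls for a minimum of 10 minutes after neostigmine administration and minimum 3 minutes after sugammadex administration before tracheal extubation". The SAP (Statistical analysis) makes the primary analysis per-protocol, so that "patients were excluded if the protocol was not followed". The primary endpoint is a single incidence, PRNB (nTOFR below 0.9) on PACU arrival, with an exact binomial interval. No comparison arm is described.

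**The concern.** The study title in the SAP refers to subjective monitoring, so the incidence is meant to show what happens when providers work without a quantitative value. If the person who has just read a low ratio is also the person reminding the provider what to do next, the value can influence care without being spoken. A reminder given with more emphasis, or at a particular moment, would be enough.

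Three features make this look serious. The blinding statement covers providers and does not say how values were kept from staff who were prompting them. The intervals before extubation have a stated minimum but no stated maximum, so a wait lengthened by such a prompt would still comply and the per-protocol exclusion would not catch it. And with one arm, any shift falls directly on the primary estimate, while the exact interval reflects sampling error only. Part of a low PRNB rate could then belong to hidden quantitative monitoring.

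**Working it through.** The documents give no figure to reproduce. The check is to take each reading in turn and ask who is named, what the value reveals, and what could still change afterwards.

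| Reading | Operator named? | What it reveals about block | What could still change the primary endpoint |
|---|---|---|---|
| Baseline | Yes, research staff | Nothing: no relaxant has been given | Nothing through this value; the device is then disconnected |
| Before reversal | No | Depth of block before reversal | Reversal and the wait that follows |
| Before extubation | No | Recovery after reversal | Timing of extubation and of departure for the PACU |
| PACU arrival | No | It is the endpoint | Nothing; averaging follows a fixed rule |

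That research staff took the last three is a reasonable inference, because Study procedures treats them as research measurements concealed from providers.

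**Intraoperative dosing.** The rocuronium formulas use height-based ideal weight, sex and age. The device is disconnected between baseline and the pre-reversal reading. Help with these calculations cannot carry a concealed value.

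**From the pre-reversal reading onward.** This is the only open window. The section Protocol bases neostigmine on ideal and sugammadex on actual body weight, and describes no use of the quantitative ratio. The provider's own tactile assessment is made at the same time. During most of the wait (at least 3 or 10 minutes, by agent) staff would hold only the pre-reversal value. A low ratio at that point is expected and does not show how far reversal has worked. The informative value comes immediately before extubation, when that decision is already at hand.

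**Steps needed for a bias.** All of these must hold:

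1. Research staff took the later readings.
2. The same individuals, not merely the same group, were prompting.
3. Prompts were given after a reading.
4. The value shaped the prompt.
5. The provider changed care or timing because of it, and the state on PACU arrival changed as a result.

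Step 1 is a fair inference. Steps 2 to 5 are not stated anywhere in the text.

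**Illustrative size.** Let p be the true PRNB incidence, a the share of cases prevented by leaked values, and b the share of non-cases turned into cases (for example, when a high ratio shortens a wait). All three are assumptions.

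Reported incidence = p(1 − a) + (1 − p)b

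| | p = 10% | p = 25% | p = 40% |
|---|---|---|---|
| a = 0, b = 0 | 10% | 25% | 40% |
| a = 10%, b = 0 | 9% | 22.5% | 36% |
| a = 20%, b = 0 | 8% | 20% | 32% |
| a = 0, b = 2% | 11.8% | 26.5% | 41.2% |

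For p = 25% and a = 10%: 0.25 × 0.90 = 0.225. For p = 25% and b = 2%: 0.25 + 0.75 × 0.02 = 0.265. The table shows that a leak would matter if it were common. It is not evidence that one occurred.

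**Would an analysis rule help?** Take an assumed 100 patients with 20 PRNB: 20% (exact 95% CI 12.7 to 29.2). Counting 5 prompted patients without PRNB as cases gives 25% (16.9 to 34.7), a bound in one direction only, although the bias could run either way. Dropping 10 prompted patients, 6 of them with PRNB, gives (20 − 6)/(100 − 10) = 14/90 = 15.6%, which is lower than 20% and so makes the result look better. Neither rule recovers the incidence without a leak.

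**The case for a change.** The strongest case for a change is that stating a blind is not the same as describing how it was kept. Disconnecting the device after baseline protects only the intraoperative period. From the pre-reversal reading on, one group label covers both those who probably know the value and those who prompt the provider, and a compliant but lengthened wait leaves no trace in the analysis set. The suggested remedy looks cheap: reversal calculations on paper before the reading, scripted reminders, a log of late prompts, and a sentence in the report.

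The descriptive part of this stands: the available text does not say who took the later readings or how values were withheld. The opening of the Protocol document and the contents of Table 1 are not available, so that detail may be given there.

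The remedy is weaker. The likeliest leak is a staff member speaking up about a low ratio just before extubation. That is safety communication, which any script would have to exempt, so the main route stays open. Reminders also support adherence. Restricting them could produce more protocol departures, and under the SAP's rule more excluded patients, which exchanges a possible small leak for a possible selection effect. Finally, both documents report conduct in the past tense, including a change of device after four patients, so procedural steps would come too late. Only the descriptive sentence is left, and it changes neither design nor analysis.

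**Conclusion.** The plan needs no change here. Followed as written, it keeps every quantitative value from the people who decide, and no passage contradicts that. The overlap of roles is an undescribed detail, not a wrong rule. The one reading expressly attributed to research staff carries no information on block depth, and exposure through the later readings requires a chain of events of which only the first link can be inferred.

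The size of any bias cannot be calculated and may be zero. Lower reported PRNB is the more plausible direction, but the opposite is possible. The percentages above rest entirely on assumed values of p, a and b.

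This conclusion rests on taking the blinding statement at its word and on the available text. It would weaken if records showed that staff routinely prompted providers after seeing a pre-extubation value. Authors would ordinarily report who measured, how values were concealed, and any overlap as a limitation. That is a reporting gap which can be filled sensibly without amending the Protocol or the SAP.

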## Study procedures

We had originally planned to use either acceleromyography (Stimpod 450, Xavant, Pretoria, South Africa) or electromyography for research measurements in this study. After trying electromyographic measurements for four patients in this study we observed that the new electromyographic monitors at our institutions had inconsistent performance. We therefore decided to exclusively use a Stimpod 450 acceleromyograph for all patients. This is a tri-axial acceleromyograph, and subsequently all measurements were obtained in the same manner for all patients. All measurements were normalized, as this is recommended when using acceleromyography.19 Two ECG surface electrodes were placed over the ulnar nerve at the wrist, with the positive electrode 3-4 cm proximal to the negative electrode. Immediately after induction of general anesthesia, and before any muscle relaxant had been administered, research staff obtained baseline TOFR measurements. The baseline and all other quantitative TOFR measurements were obtained by averaging two measurements separated by at least 15 s. If the initial two measurements were not within 10% agreement, additional measurements (up to four total) separated by at least 15 s were made and the two closest TOF ratios averaged. Anesthesia providers were blinded to all quantitative measurements. After baseline measurements, the research staff disconnected the Stimpod 450, but left the surface electrodes in place to be used for subsequent study measurements. Additional measurements were obtained in duplicate immediately before reversal when the anesthesia provider made the tactile pre-reversal assessment, immediately before tracheal extubation, and a final set of measurements were obtained within 5 min of arrival to the post anesthesia care unit (PACU).

Baseline measurements were used to normalize all subsequent measurements. This was done to correct for the inflated TOFR values that are usually obtained by acceleromyography. 20,21 As an example, if the baseline TOFR is 1.15 and the raw postoperative TOFR is 0.95, then the nTOFR is 0.95/1.15 =0.83. Normalization usually yields lower TOF ratios, and it is more likely to classify observations as positive for PRNB. Therefore, the incidence of PRNB is typically higher when comparing normalized to non-normalized (also referred to as "raw") measurements. PRNB was defined as a nTOFR <0.9 on arrival to the PACU.

Study Title: Best Practice With Rocuronium, Neostigmine, Sugammadex, and Subjective Monitoring

NCT03543826

Document title: Statistical Analysis Plan

Date of the document: 5/8/2019

Statistical analysis

We present descriptive statistics [mean (standard deviation) or frequencies] for baseline measures of patient and surgery characteristics. The primary endpoint, incidence of PRNB (nTOFR <0.9) on arrival to the PACU, was calculated with exact binomial 95% confidence interval, and graphically displayed using scatterplots. The primary analysis was "per-protocol" and patients were excluded if the protocol was not followed. Secondary endpoints included severe PRNB, defined as nTOFR <0.7 on arrival to the PACU, and PRNB at time of tracheal extubation (nTOFR <0.9). These were also calculated with the exact confidence intervals. Additionally, we calculated the incidence of severe PRNB at time of tracheal extubation and the incidence of PRNB using raw (non-normalized) measurements.

We compared the duration between end of surgery and arrival to the PACU for patients whose tracheas were extubated in the OR and those extubated in PACU. We also compared the duration between end of surgery and arrival to the PACU for patients receiving sugammadex or neostigmine.

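### Does pooling patients extubated in the OR with those extubated in the PACU distort the PACU-arrival PRNB incidence?

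*SAP*

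**What the plan says.** The protocol (Study procedures) ties the endpoint to arrival alone: "PRNB was defined as a nTOFR <0.9 on arrival to the PACU". Readings are taken before reversal and immediately before extubation, and then "a final set of measurements were obtained within 5 min of arrival to the post anesthesia care unit (PACU"). For a patient who arrives still intubated, the order of the last two readings is not spelled out.

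The protocol (Protocol section) asks for a "minimum of 10 minutes after neostigmine administration and minimum 3 minutes after sugammadex administration before tracheal extubation". It attaches no place to that wait.

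The SAP (Statistical analysis) gives the primary result as one figure: "The primary endpoint, incidence of PRNB (nTOFR <0.9) on arrival to the PACU, was calculated with exact binomial 95% confidence interval". Severe PRNB on arrival (nTOFR below 0.7) is treated the same way. The SAP adds "PRNB at time of tracheal extubation (nTOFR <0.9") and severe PRNB at extubation. The analysis is per-protocol: "patients were excluded if the protocol was not followed". Nothing describes extubation in the PACU as a departure from protocol. Place of extubation appears once, where time from end of surgery to PACU arrival is compared "for patients whose tracheas were extubated in the OR and those extubated in PACU". The same duration is compared by reversal drug: "We also compared the duration between end of surgery and arrival to the PACU for patients receiving sugammadex or neostigmine".

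**The concern.** A patient extubated in the OR under the protocol has completed the minimum wait after reversal before reaching the PACU, provided that the wait counts as a per-protocol criterion. A patient who arrives intubated carries no such assurance. The arrival reading, due within 5 minutes, could fall before extubation and inside the wait. A value below 0.9 would then mean that reversal was still in progress, whereas in a patient extubated in the OR it means block left over after the airway was removed.

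At stake is how the headline incidence is read. With a single pooled figure, a reader cannot tell whether patients not yet extubated contribute to it. The SAP already recognises the two groups, so the absence of a PRNB breakdown looks like an omission.

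**Working it through.** The documents give no sample size, no number extubated in the PACU, no reversal-to-arrival interval and no expected incidence. There is no plan figure to reproduce. The check is whether the pooled figure is wrong, how large the effect could be, and whether a breakdown would resolve it.

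**1. Estimand against estimator.** The protocol defines PRNB by the arrival value with no airway condition. The SAP counts patients meeting that definition and attaches an exact binomial interval. The two agree. The incidence analyses contain no between-group contrast that the mixture could bias.

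**2. When a reading can fall inside the wait.** Let T be the time from reversal to arrival (reversal assumed to be given before arrival), r the time from arrival to the reading (0 to 5 min, protocol) and W the minimum wait (10 or 3 min, protocol). The reading is inside the wait only if T + r < W, that is T < W − r.

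| Drug | r = 0 | Intermediate r | r = 5 |
|---|---|---|---|
| Neostigmine, W = 10 | T < 10 | r = 3: T < 7 | T < 5 |
| Sugammadex, W = 3 | T < 3 | r = 2: T < 1 | not possible (nor for any r ≥ 3) |

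The issue is therefore mainly about neostigmine. It needs several things together: extubation in the PACU, an arrival reading before extubation, a short T, and a value below 0.9 because of that timing. None of these frequencies is in the documents. The protocol lists the arrival reading last and calls it the final set, which suggests that it usually followed the pre-extubation reading. This does not settle the order for patients who arrived intubated.

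**3. Effect on the pooled figure.** If a share f is extubated in the PACU, pooled incidence = (1 − f) × p_OR + f × p_PACU, so it differs from the OR rate by f × (p_PACU − p_OR). On assumed rates p_OR = 20% and p_PACU = 50%:

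- f = 5%: 0.95 × 20 + 0.05 × 50 = 21.5%
- f = 10%: 23%
- f = 30%: 29%
- f = 50%: 35%

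With p_PACU = 10%, the shift runs from −0.5 points (f = 5%) to −5 points (f = 50%). With equal rates it is zero. These shifts reflect who is in the population, and case mix or reversal drug could produce them as readily as timing.

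**4. Ceiling on the timing part.** If k of x positive arrival readings preceded extubation, removing all of them leaves (x − k)/n. Assumed n = 100, x = 20, exact 95% intervals:

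| k | Remaining incidence | 95% CI |
|---|---|---|
| 0 | 20% | 12.7 to 29.2% |
| 2 | 18% | 11.0 to 26.9% |
| 5 | 15% | 8.6 to 23.5% |
| 10 | 10% | 4.9 to 17.6% |

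Since k cannot exceed the number m extubated in the PACU, early measurement explains at most m/n of the incidence. The duration comparison already needs m.

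**5. What a breakdown would show.** Keep 20/100 and assume 20 PACU extubations. The split could be 8/20 = 40% (19.1 to 63.9%) against 12/80 = 15% (8.0 to 24.7%). It could equally be 2/20 = 10% (1.2 to 31.7%) against 18/80 = 22.5% (13.9 to 33.2%). Place was not randomised, so neither pattern isolates timing. Counting readings taken before extubation does not isolate it either: a patient may arrive intubated well past the wait, so that count only bounds from above the number of readings inside the wait. The interval from reversal to reading is what would test the mechanism.

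**The case for a change.** The strongest case for a change is that the extubation-time endpoints are pooled too, so they do not show how many positive arrival readings came from intubated patients. The arrival figure is the primary result. The OR/PACU grouping is already used in the SAP, and a table by place with exact intervals needs no new measurement.

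The textual part of this stands: no breakdown is planned, and the order of readings for patients who arrive intubated is not stated. The low cost also stands. The step from there to a needed change does not. The extubation-time endpoints already assess patients at the same clinical event wherever it happens, so a reader who doubts the arrival figure has a parallel estimate. The extra table would leave the primary endpoint, its interval and every secondary endpoint as they are, and it would not separate early measurement from case mix. An order-of-readings count depends on recorded times, which the documents do not mention. Finally, the timing effect can only push the incidence up, so it could not make the protocol look better than it is.

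**Conclusion.** No change to the plan is needed. The pooled arrival incidence and its exact interval are correct for the endpoint as defined, and the planned extubation-time endpoints cover most of the interpretive worry. The size of any timing effect is not computable from the documents. It may be zero, is capped at k/n, and runs against the protocol; other differences between the two groups could act in either direction. The counts and rates used for scale above are assumed, and the contrast with patients extubated in the OR assumes that the minimum wait was a per-protocol criterion.

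What remains is optional. The report could give the number extubated in each place, arrival PRNB and severe PRNB by place as description only, and, where times were recorded, the order of the readings and the reversal-to-reading interval by drug. Leaving this to the analysts is a fair choice.

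### The primary PRNB incidence is planned only for patients in whom the protocol was followed; a companion figure for all enrolled patients should be reported beside it

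*SAP*

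**What the plan says.** The SAP, under Statistical analysis, makes PRNB on arrival in the PACU the primary endpoint and reports it as a single proportion with an exact 95% interval. It then fixes the population: "The primary analysis was 'per-protocol' and patients were excluded if the protocol was not followed". The remaining planned incidences are severe PRNB in the PACU, PRNB and severe PRNB at extubation, and PRNB on raw readings. They change the threshold, the time point or the normalisation; none is said to bring excluded patients back. The only comparisons planned are of durations, by place of extubation and by reversal drug.

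The Protocol section contains firm steps. One is that "a tactile pre-reversal assessment of the thumb response to ulnar nerve stimulation was mandatory"; another is a "minimum of 10 minutes after neostigmine administration and minimum 3 minutes after sugammadex administration before tracheal extubation". It justifies some steps by their bearing on PRNB. The change to ulnar nerve stimulation at the end of the procedure is made "to mitigate against eye-muscle monitoring as a significant risk factor for PRNB", and the age-related dose reduction is explained "with age being a known risk factor for PRNB".

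Under Study procedures, "Baseline measurements were used to normalize all subsequent measurements", so a patient needs both a baseline and a PACU reading to contribute to the endpoint.

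**The concern.** Patients are removed after enrolment because of what happened during their anaesthetic. If departures from the protocol were unrelated to PRNB, removing those patients would cost only sample size. The protocol's own reasoning makes that doubtful: where a step exists because its omission is thought to raise PRNB risk, patients in whom it was omitted may have a different PRNB rate from those kept.

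No comparison arm for PRNB is described, so the headline is one proportion and any selection enters it directly. The exact interval reflects sampling error among the patients kept and says nothing about those taken out. At stake is which population the figure describes: patients who received the package as specified, or all patients enrolled to receive it. With the planned output alone, a reader could not tell how far apart the two rates are.

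**Working it through.** **Check of the text.** In the text available for review, per-protocol is the only population named for the primary endpoint, and no all-enrolled or sensitivity population appears. The documents give no enrolment figure, exclusion count or expected PRNB rate, so there is no figure of the plan's own to reproduce.

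**Inputs, all assumed.** 100 patients enrolled, all with a usable nTOFR; reported (per-protocol) rate p = 10%; excluded share f = 10% or 20%; RR = PRNB risk in excluded relative to kept patients = 0, 1, 2 or 4.

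**Formula.** All-enrolled rate = (1 - f) x p + f x RR x p. Hence reported minus all-enrolled = f x p x (1 - RR). Example: f = 0.20, RR = 4 gives 0.20 x 0.10 x (1 - 4) = -0.06, or -6 points.

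**Results** (Clopper-Pearson 95% intervals):

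| Reported set | RR | PRNB among excluded | All-enrolled rate (95% CI) | Reported minus all-enrolled |
|---|---|---|---|---|
| 9/90 = 10.0% (4.7 to 18.1) | 0 | 0/10 | 9/100 = 9.0% (4.2 to 16.4) | +1 point |
| | 1 | 1/10 | 10/100 = 10.0% (4.9 to 17.6) | 0 |
| | 2 | 2/10 | 11/100 = 11.0% (5.6 to 18.8) | -1 |
| | 4 | 4/10 | 13/100 = 13.0% (7.1 to 21.2) | -3 |
| 8/80 = 10.0% (4.4 to 18.8) | 0 | 0/20 | 8/100 = 8.0% (3.5 to 15.2) | +2 |
| | 1 | 2/20 | 10/100 = 10.0% (4.9 to 17.6) | 0 |
| | 2 | 4/20 | 12/100 = 12.0% (6.4 to 20.0) | -2 |
| | 4 | 8/20 | 16/100 = 16.0% (9.4 to 24.7) | -6 |

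The difference scales with the reported rate. At f = 10%, RR 0, 2 and 4 give +0.5, -0.5 and -1.5 points for a reported rate of 5%, and +2, -2 and -6 points for 20%.

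**Does the reported interval bound the difference?** Every all-enrolled rate in the table lies inside the reported interval, but nothing in the method guarantees this. Take 200 enrolled, 40 excluded and 24/160 = 15.0% reported (9.9 to 21.5). The all-enrolled rate can lie anywhere from 24/200 = 12.0% to 64/200 = 32.0%. The upper end needs PRNB in all 40 excluded patients and is an extreme. If the excluded patients had double the risk (12 of 40), the rate would be 36/200 = 18.0%, inside the interval.

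**The case against.** The per-protocol choice is openly stated and answers a sensible question: how often PRNB occurs when the package is delivered. No randomised comparison is described that exclusions could break. The Protocol section says providers were trained and that research staff helped with reminders and dose calculations, which may keep exclusions few, particularly for the age-related dose reduction. Study procedures says providers did not see the quantitative readings, so their departures were not responses to the study nTOFR. The size is hypothetical and modest: with 10% excluded and doubled risk, it is 1 point.

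All of this stands, and it limits the weight of the point. It does not remove it. Departures can follow patient or surgical risk without any sight of the readings, and a small excluded share is a reason to expect a small difference, not a report of it. The word primary might hint at a further analysis, but none is described.

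Three stronger readings are tempting and unsupported:

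- A reader might infer that the reported rate will be too low. That is plausible, but RR may be below, at or above 1, and the documents do not say which.
- A reader might infer that the plan never defines non-adherence, since some steps are only recommended. Table 1, which the protocol cites, and part of the protocol were not in the text available for review, and a definition may be there.
- A reader might add the switch of monitor ("After trying electromyographic measurements for four patients in this study"). A change of device is not non-adherence, and the same section then describes one device for every patient. How those four were handled is a separate matter of detail and not evidence for this point.

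**Conclusion.** The point holds as a cheap improvement. The SAP limits the primary incidence to patients in whom the protocol was followed, and no PRNB incidence in all enrolled patients is planned in the text available. Because the protocol ties some of its steps to PRNB risk, equal risk in kept and excluded patients is an assumption that should be checked.

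The illustrated range of +2 to -6 points rests wholly on assumed values for the reported rate, the excluded share and the relative risk, and on every enrolled patient having a usable reading. It shows what could happen; it does not demonstrate a large bias or its sign. Nor is the per-protocol analysis invalid. What is missing is the companion estimate that would show whether the distinction between the two populations matters here.

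**What to change.** Keep the per-protocol incidence as it is. Beside it, report PRNB incidence with an exact 95% interval in all enrolled patients who have usable baseline and PACU nTOFR readings, regardless of adherence. Give the number excluded for not following the protocol and their PRNB rate, and the number of enrolled patients without usable readings. That last count is needed because requiring readings is itself a selection after enrolment.

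The cost is a sentence in the SAP, one further exact proportion and a few counts; no treatment or measurement changes. There are two downsides. The second figure may be less favourable than the first. It is also available only where excluded patients were measured, which the documents do not confirm; if they were not, the report should say so.
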